7.6.4. Blinding and Unblinding Rules

A randomization table will be kept with the sponsor. Subjects and study site staff (investigators, researchers, care providers) will be blinded to the group assignment. Personnel involved in device placement will not be involved in subject care or study outcome data collection to avoid any potential bias. Should a subject experience an adverse event and the investigator deems unblinding necessary for appropriate care, the subject and research staff will be unblinded and the subject will be withdrawn from the study.

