7.6.8. Device Removal

Medical staff trained and delegated will remove the Bridge device on Day 6. The device shall be disposed in a Sharps container, in accordance with Masimo's Bridge Device Training program, the Device Instructions for Use (DFU) and Operator's Manual.

If subject requests to remove the Bridge device prior to 5 days, they will be withdrawn from further study assessments and procedures, however their data collected up to the point of withdrawal may still be used for data analysis.

CLINICAL INVESTIGATION PLAN

Impact of Bridge™ device as a non-pharmacological approach to treat opioid withdrawal in opioid use disorder (OUD) subjects in an inpatient treatment center

DENE0001

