8. STATISTICAL DESIGN AND ANALYSIS

This is a single site, two-arm, prospective, randomized, double-blind, sham-controlled clinical trial. The study's main outcomes are COWS and subjective opiate withdrawal scale (SOWS) scores, measured over 8 time periods: at baseline, 30, 60, 120 minutes, 2nd, 3rd, 4th, and 5th day.

The study design data results in correlated observations will be collected repeated measurements within clusters (i.e., patients). These correlations invalidate the independence assumption in commonly used univariate and multivariate statistical techniques such as t-tests and multiple linear regression. Therefore, the Generalized Estimating Equations (GEE) method was used to estimate the power and sample size, a flexible class of models that account for correlated observations and are a commonly used method for repeated data analysis. This class of model does not require the normality assumption and does not require the full specification of the joint distribution of repeated measurements. Further, the power/sample size for testing the time-averaged difference (TAD) between two means from continuous, correlated data that will be analyzed using the GEE method was calculated. Such data occur in two design types: clustered and longitudinal (repeated measurement). Time-averaged difference analysis is often used when the outcome to be measured varies with time.

The following parameter estimates are required for calculating the power:

1. Alpha (α): The probability of rejecting a true null hypothesis = 0.05
2. δ : The time-averaged difference at which the power is calculated. We estimated that the COWS time average is 2.8 for the Bridge group and 6.8 for the sham group, then $\delta = 4.0$.

The δ of 4.0 was selected such as to be conservative and taking into consideration:

Impact of Bridge™ device as a non-pharmacological approach to treat opioid withdrawal in opioid use disorder (OUD) subjects in an inpatient treatment center

DENE0001

- After the first two hours comfort medications and medication tapers may be administered to the control group thus the COWS score may be reduced
- After three days the withdrawal symptoms are anticipated to abate for both groups

The above rationale was discussed with and supported by Masimo Bridge device and OUD clinical experts.

The power was calculated for various TAD δ values 2.8, 3, 4 and 4.7 (see Figure 3).

3. σ : The standard deviation of a response (COWS): 5.047 (estimated, see Table 2 below).

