4. ρ : The base correlation between two responses on the same subject. We used the estimate calculated by the other statistician for the sample size calculation (0.40).
5. The treatment group allocation proportion is the proportion of subjects that are in the treatment group. The proportion is 1:1 (50%)
6. The number of time points at which each subject is measured: 9.
7. The time values represent the proportion of the total study time that has elapsed just before the measurement: 0, 0.003, 0.005, 0.01, 0.021, 0.25, 0.5, 0.75, 1, which are equivalent to: prior to device placement, 20 min, 30 min, 60 min, 120 min, 2nd day, 3rd day, 4th day and 5th day.

Data used for the sample size calculation was abstracted from the article by Adrian Miranda & Taca (2018)⁵.

Table 2. COWS Score Statistics Based on Article by Adrian Miranda & Arturo Taca (2018)⁵

Time (mins)	BRIDGE Group			
	Mean COWS	% Reduction	SD	n
0	20.1	0.0	6.1	73
20*	7.5	62.7	5.9	62
30	4.0	80.1	4.4	73
60	3.1	84.6	3.4	71
120	2.8	86.1	**	
1440 (Day 2)	2.1	89.6	**	
2880 (Day 3)	1.4	93.0	**	
4320 (Day 4)	1.0	95.0	**	
5760 (Day 5)	0.6	97.0		33
Average	2.8	86.0		
Pooled SD		5.047		

* 20 minutes measurement is not included in the study design; it was included from the article to enhance the estimates for the required parameters for the sample size/power calculations.

** The yellow highlighted values are estimated (extrapolated from the available data)

A sample of 32 subjects (16 in each group), each measured 9 times, achieve a power of 0.9068 when using a two-sided Wald test from a GEE analysis to test whether the time-average difference of the Bridge subjects differs from that of the sham subjects by more than 4.0 at a significance level of 0.05. The subjects are randomly split between a

[figure not shown]
Impact of Bridge™ device as a non-pharmacological approach to treat opioid withdrawal in opioid use disorder (OUD) subjects in an inpatient treatment center**DENE0001**

Bridge group and a sham group, with 50% of the subjects assigned to the Bridge group. The residual standard deviation is anticipated to be 5.04729. The measurements of each subject will be made at the following times expressed as proportions of the total study time: 0, 0.003, 0.005, 0.01, 0.021, 0.25, 0.5, 0.75, 1, which are equivalent to: prior to device placement, 20 min, 30 min, 60 min, 120 min, 2nd day, 3rd day, 4th day and 5th day. Missing values are assumed to occur completely at random (MCAR).

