Anticipating a 50% drop out and missing COWS evaluation rate, 48 participants (24 in each arm) should be enrolled into the study to guarantee a minimum of 32 participants who complete the COWS evaluation and the study.

Figure 3 below shows the relationships of power and sample size for the various δ s.

Figure 3. Power versus Sample Size for δ of 2.8, 3.0, 4.0 and 4.7

A separate Statistical Analysis Plan has been developed for this study.

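### Enrolling 48 does not guarantee 32 completers at the plan's own 50% loss: it leaves 24, for which completer-based power is about 0.81

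*Combined protocol and SAP*

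**What the plan says.** Section 8 (Statistical Design and Analysis) first gives the power: "A sample of 32 subjects (16 in each group), each measured 9 times, achieve a power of 0.9068", for a time-averaged COWS difference of 4.0 tested with a two-sided Wald test from a GEE model at 0.05. It then moves from the 32 analysed to the number enrolled: "Anticipating a 50% drop out and missing COWS evaluation rate, 48 participants (24 in each arm) should be enrolled into the study to guarantee". What this enrolment is said to secure is "a minimum of 32 participants who complete the COWS evaluation and the study". The synopsis (Section 2) also gives 48 as the total.

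Three other provisions bear on the point.

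- **Replacement.** Section 7.5.4 allows, but does not require, another participant to be recruited when one leaves or is withdrawn.
- **Partial data.** Section 7.6.8 says of participants who ask for early device removal that "their data collected up to the point of withdrawal may still be used for data analysis".
- **Analysis rules.** Section 8 ends with "A separate Statistical Analysis Plan has been developed for this study". That separate plan is not among the documents supplied.

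**The concern.** The drop-out sentence contradicts itself. If half of those enrolled drop out or lack COWS evaluations, 48 enrolled cannot be expected to give 32 completers, still less guarantee them. The figure of 48 appears to come from multiplying 32 by 1.5 instead of dividing 32 by the retained fraction.

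This sentence is the only link between the 0.9068 and the enrolment of 48. A reader or IRB would take from it that power of about 0.91 is protected against a 50% loss. On the plan's own completer basis the type II error at that loss is about 0.19, against 0.09 as stated.

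The 50% cannot simply be read as a slip for 33%. Of the inputs, Section 8 says "Data used for the sample size calculation was abstracted from the article" that it cites, and in Table 2 the number observed falls from 73 at time 0 to 33 at Day 5.

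**Working it through.** **Inputs, all from Section 8:** δ = 4.0 (2.8 against 6.8); SD = 5.04729; within-subject correlation ρ = 0.40; two-sided α = 0.05; 1:1 allocation; m = 9 measurements in the power calculation; anticipated loss 50%; enrolment 48; completers required 32. The study schedule itself has 8 assessments ("measured over 8 time periods: at baseline, 30, 60, 120 minutes, 2nd, 3rd, 4th, and 5th day"); the 20-minute time was added only for the calculation.

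**1. Reproduce the stated power.** For n per arm and m equally correlated measurements,

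SE = SD × √[2(1 + (m − 1)ρ)/(m n)], power = Φ(δ/SE − 1.96).

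With n = 16 and m = 9: (1 + 8 × 0.4)/9 = 0.4667; SE = 5.04729 × √(2 × 0.4667/16) = 1.219; 4.0/1.219 − 1.96 = 1.321; power = 0.9068. This matches the plan to four decimals, so equal correlation with a normal-theory Wald test is taken as its method.

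**2. Enrolment arithmetic.**

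- Completers at 50% loss: 48 × (1 − 0.5) = 24, or 12 per arm, a shortfall of 8.
- Origin of 48: 32 × 1.5 = 48.
- Enrolment that matches a 50% loss: 32/(1 − 0.5) = 64.
- Largest loss at which 48 still yields 32: 1 − 32/48 = 33.3%.

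**3. The guarantee.** Assume each participant is lost independently. With loss probability 0.5, the chance that at least 32 of 48 complete is 0.0147 (1.5%). With loss probability 1/3 it is 0.567 (57%), so even then 32 is an expected number and not a minimum.

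**4. Table 2 as a guide to loss.** 1 − 33/73 = 54.8%; 48 × 33/73 = 21.7, or about 22 remaining. These counts are only a rough guide: n is 62 at 20 minutes and 73 again at 30 minutes.

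**5. Power with 12 completers per arm, same method.**

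| Measurements per completer | SE | Power |
|---|---|---|
| 9 (as in the plan's calculation) | 1.408 | 0.811 |
| 8 (as scheduled) | 1.420 | 0.804 |
| 7 (scheduled, without baseline) | 1.436 | 0.795 |

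**6. What partial data could add.** Count only post-baseline scores, keep δ, ρ and MCAR as the plan assumes, and weight participants by their information. Twelve completers per arm with 7 scores contribute 12/0.4857 = 24.71.

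- Twelve dropouts per arm with one score each add 12/1 = 12. Total 36.71; SE = 5.04729 × √(2/36.71) = 1.178; power = 0.924.
- With three scores each (30, 60 and 120 minutes), (1 + 2 × 0.4)/3 = 0.6, so they add 12/0.6 = 20. Total 44.71; SE = 1.068; power = 0.963.
- Dropouts with only a pre-placement score add essentially nothing, because no treatment effect can be present before placement.

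**The case against.** The strongest reply is that 0.81 is a low figure. It treats every lost participant as contributing nothing, whereas GEE under the plan's MCAR assumption can use whatever scores exist. On that basis one post-baseline score per dropout, the first being due at 30 minutes, already takes power to 0.924, above the stated 0.9068. That stands as a statement about power, and it is why this point does not claim the trial is too small. It does not rescue the sentence, which counts people who complete; partial data add none. The power gain also needs a rule that the supplied text does not contain. Section 7.6.8 says only that such data may be used, and only for participants who request early removal. It does not cover discontinuation at the investigator's discretion (Section 7.5.4) or withdrawal after unblinding, where "the subject and research staff will be unblinded and the subject will be withdrawn from the study". The separate SAP may settle this.

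A second reply is that 50% means 50% of the 32 required, that is, 16 extra. This gives 48 exactly, but the text calls it a drop-out and missing-evaluation rate, which ordinarily refers to those enrolled. Even on that reading the loss among those enrolled is 33%, and 32 is not guaranteed.

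A third is replacement. It is optional, is not part of the calculation, and at a 50% loss would mean enrolling about 64 against a stated total of 48.

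Finally, the Table 2 counts come from a study whose title describes a retrospective assessment, so they may reflect which records were available and not drop-out. That is fair, and they are used here only to show that the plan's source does not point to 33%.

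**Conclusion.** The concern holds. At the plan's own 50% loss, 48 enrolled leaves about 24 completers (12 per arm), 8 fewer than the stated minimum of 32. The matching completer-based power is 0.811 by the plan's method, or 0.804 with the scheduled 8 assessments, against 0.9068. Leaving out the baseline score gives 0.795, an immaterial difference.

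The completer counts follow directly from the plan's figures. The power figures rest on its δ, SD and ρ, with equal correlation inferred because it reproduces 0.9068. The 1.5% and 57% chances rest on independent losses, which is an assumption made here. Power in the final analysis could be well above 0.81 if dropouts' post-baseline scores are analysed; how far depends on the drop-out pattern and on a rule that the supplied text leaves open. The point should be corrected, but it does not show that the trial is underpowered.

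**What to change.** Keep enrolment at 48, remove the guarantee, and replace the drop-out sentence in Section 8 with wording such as:

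> With an anticipated 50% loss to drop-out or missing COWS evaluations, the 48 participants enrolled (24 per arm) are expected to yield about 24 completers (12 per arm). On this completer basis, power for a time-averaged difference of 4.0 is about 0.81 (0.80 with the 8 scheduled time points).

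If the sponsor in fact expects a loss of 33% or less, it should replace the 50% and justify the new rate against the fall from 73 to 33 in Table 2. If replacement under Section 7.5.4 is meant to supply completers, the plan should say so and reconcile it with the total of 48.

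If the sponsor wishes to claim power from partial data, that claim should rest on a firm rule that covers all randomised participants, whatever the reason for leaving, and should count only post-baseline scores as carrying the effect.

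The cost is one rewritten sentence, with no extra participants and no change to procedures.

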9. DATA MANAGEMENT

9.1. Data Management and Confidentiality

All documents associated with this protocol will be securely stored in a physical location or on password-protected computers. The confidentiality and retention of these documents will be protected to the extent provided and required by the law. All data will be de-identified before any statistical analysis. Only de-identified data will be shared with Masimo for research purposes stated in this protocol. Data collected by the eCRF data capture software will be shared with Masimo via a secure, password-protected server that only research staff, and Masimo study team members will have access to. Data will be retained for a minimum of two years following completion of the final analysis.

CLINICAL INVESTIGATION PLAN

Impact of Bridge™ device as a non-pharmacological approach to treat opioid withdrawal in opioid use disorder (OUD) subjects in an inpatient treatment center
DENE0001

9.2. Source Documents

Source data is all information, original records of clinical findings, observations, or other activities in a clinical trial necessary for the reconstruction and evaluation of the trial. Source data are contained in source documents. Examples of these original documents and data records include hospital records, clinical and office charts, laboratory notes, memoranda, recorded data from automated instruments, and copies or transcriptions certified after verification as being accurate and complete.

9.3. Case Report Forms

The site shall capture study data in case report forms (CRFs) for each subject enrolled, to be provided to the sponsor. CRFs may be in paper or electronic format through electronic data capture (EDC) software. Masimo shall ensure that systems used for electronic CRFs are compliant with the requirements of 21 CFR Part 11 and ISO / IEC 27001 certification. The CRFs will be completed and signed by the PI or delegate. This also applies to those participants who fail to complete the study.

If a participant withdraws from the study, the reason must be noted on the CRF. The eCRFs are to be completed on an ongoing (weekly) basis. CRF entries and corrections will only be performed by study site staff, authorized by the investigator. For paper CRFs, entries and corrections to the CRF will be made following good documentation practices (GDP).

The CRF may include the following information, including but not limited to: inclusion/exclusion criteria, whether participant consent was obtained before start of study, demographic information, device readings, and if occurrence of any adverse event, protocol deviation, and device deficiencies, etc. The CRFs will be signed by the PI or delegate to attest that the data are complete and accurate.

CRF entries will be checked by the study monitor and any errors or inconsistencies will be queried to the site on an ongoing basis. Any changes made within an electronic CRF will be tracked by audit trail. Any changes on a paper CRF will be made directly on the CRF and will be initialed and dated by the person making the change. Query resolution will be assessed and confirmed by study monitor during site visit.

9.4. Data Transfer and Storage

Original paper CRFs will be stored in a secure location at the site. Copy of the original paper CRFs may be scanned and sent to sponsor. If using electronic CRFs, the site staff will be assigned unique usernames and passwords for data security. Final copies of the electronic CRFs in EDC are stored on a secure server.

Only authorized sponsor personnel will have access to study data and will move it to a secure and backed-up drive at Masimo.

CRFs will be checked for completeness and if there are inconsistent or missing data points, queries will be generated. If delegated research staff are to correct the paper CRF, they shall follow GDP practices to strike through old entry, add in new entry, initial and date it, and provide the corrected information to sponsor. Corrections made to electronic CRFs will be tracked by audit trail and require PI or delegate sign-off.

CLINICAL INVESTIGATION PLAN

Impact of Bridge™ device as a non-pharmacological approach to treat opioid withdrawal in opioid use disorder (OUD) subjects in an inpatient treatment center

DENE0001

9.5. Record Retention

Study data will be retained for the necessary period of time as required by the institution's regulations. Study records shall be retained for a minimum of two years after study closure. The institution's own retention policies and regulations may apply in addition to the minimal requirement.

10. AMENDMENTS TO THE CLINICAL INVESTIGATION PLAN

Any changes made to the clinical investigational plan/study protocol will be documented by way of an amendment. Before submitting a protocol amendment to the IRB, the protocol amendment must be agreed upon and signed by both the PI and the sponsor. The protocol amendment will be submitted to the IRB for approval. At a minimum, a redline version and a clean version of the new protocol amendment will be kept on file by the PI and the sponsor. Protocol amendments will need to be version controlled. Both PI and sponsor will retain the IRB approval letter as confirmation that the protocol amendment was approved.

11. DEVIATIONS FROM CLINICAL INVESTIGATION PLAN

Deviations from the protocol must receive both sponsor and the investigator's IRB/ethics committee approval before they are initiated, with the exception that under emergency circumstances, deviations from the *Clinical Investigation Plan* to protect the rights, safety and well-being of human participants may proceed without prior approval of the sponsor or the IRB/ethics committee.

Any protocol deviations initiated without sponsor and the investigator's IRB/ethics committee approval that may affect the scientific soundness of the study, or affect the rights, safety, or welfare of study participants, must be documented and reported to the sponsor and to the investigator's IRB/ethics committee as soon as a possible, but no later than 5 working days after the occurrence of the protocol deviation. In addition to documenting deviations on the CRF, the *Protocol Deviation Form* may also be used. If protocol deviations continue to occur frequently at a study site, a corrective and preventive action (CAPA) may be opened by the sponsor.

Withdrawal of IRB approval: An investigator shall report to the sponsor a withdrawal of approval by the investigator's reviewing IRB as soon as possible, but no later than five working days of the IRB notification of withdrawal of approval.

12. DEVICE ACCOUNTABILITY

12.1. Receipt of Study Device

Upon receipt of the study device supplies, an inventory must be performed, and the device accountability log filled out and signed by the person accepting the shipment. It is important that the designated research staff counts and verifies that the shipment contains all the items noted in the shipment inventory. Any damaged or unusable study devices in a given shipment will be documented in the study files. The investigator must notify the study sponsor of any damaged or unusable study devices that were supplied to the investigator's site.

12.2. Use of Study Device

Use of device will be documented in a CRF module for each participant. Any unused devices must be returned to the sponsor at the end of the study or before product expiration date.

CLINICAL INVESTIGATION PLAN

Impact of Bridge™ device as a non-pharmacological approach to treat opioid withdrawal in opioid use disorder (OUD) subjects in an inpatient treatment center

DENE0001

12.3. Return or Destruction of Study Device

At the completion of the study, there will be a final reconciliation of study devices shipped, devices used, and devices remaining. This reconciliation will be logged on the device accountability log. Any discrepancies noted will be investigated, resolved, and documented prior to return or destruction of unused study devices. Devices destroyed onsite will only be upon written instruction from the sponsor and will be documented in the study files. When a Masimo device deficiency is observed, every effort should be made to return the device and its packaging to the Sponsor in a timely manner.

13. STATEMENTS OF COMPLIANCE

This document is a clinical investigational plan for a human research study sponsored by Masimo Corporation. The study will be conducted in accordance with the ethical principles that have their origin in the Declaration of Helsinki. By participating in the study, the Investigator agrees to adhere to all stipulations of this protocol, the conditions of the IRB or REC approval, federal and local regulatory requirements, 21 CFR 812, ISO-14155, ICH GCP guidance.

The protocol, ICFs, recruitment materials, and all participant materials will be submitted to the IRB for review and approval. Approval of both the protocol and the consent form must be obtained before any participant is enrolled. Any amendment to the protocol will require review and approval by the IRB before the changes are implemented to the study.

